SAE	serious adverse event
SAP	Statistical analysis plan
SCS	Systemic corticosteroids
SD	standard deviation
SGRQ	St George's Respiratory Questionnaire
SOC	System Organ Class
TFLs	Tables, Figures, Listings
TBL	total bilirubin
T _{max}	time to reach maximum (peak) plasma concentration following drug administration
ug	microgram
ULN	upper limit of normal
TFLs	Tables, Figures, Listings

1 Introduction

This document contains details of the statistical methods that will be used in the Phase 2b clinical trial CQBW251B2201. The purpose of this Phase 2b study is to support the dose selection for future studies by evaluating efficacy and safety of different QBW251 doses in COPD patients with chronic bronchitis and a history of exacerbations, compared to placebo, when added to a triple combination therapy of LABA/LAMA/ICS. Lung function improvement will be the primary endpoint: trough FEV₁ change from baseline after 12 weeks of treatment.

Data will be analyzed according to Section 12 of the study protocol.

Important information is given in the following sections and details are provided, as applicable, in [Section 5](#).

1.1 Study design

[figure not shown]
This study uses a 6 treatment arm, parallel-group, randomized, double-blind study design. One treatment arm (450 mg b.i.d.) was discontinued after reaching a pre-defined stopping criterion (see Section 12.7.1 of the protocol) at the first DMC interim analysis.

Patients initially undergo a screening period of 1 week. This screening period (Weeks -3 to -2) serves to assess eligibility and to taper patients off disallowed medications. Subsequently, patients enter the run-in period (2 weeks; Days -14 to 1) to establish baseline values for symptom assessments, to standardize the COPD background therapy (triple combination LABA/LAMA/ICS), and to complete eligibility assessments. At visit Run-In 2 final eligibility will be assessed. Eligible patients will move into the Day 1 visit where they will be randomized. Day 1 also generates additional baseline data and study treatment is initiated. The treatment period consists of 24 weeks, during which the patient returns to the site for regular visits (Day 1 – Week 24). Upon completion of the treatment period, patients are followed up for safety assessments during the Follow-Up period (Weeks 25 – 28).

Approximately 956 male and female COPD patients are randomized into 1 of 6 treatment arms with a randomization ratio of 2:2:1:1:1:2 (450 mg b.i.d. (discontinued), 300 mg b.i.d., 150 mg b.i.d., 75 mg b.i.d., 25 mg b.i.d., placebo). Detailed information regarding sample size calculation is provided in [Section 3](#). After reaching the pre-defined exposure-based stopping criterion, patients were no longer randomized to the 450 mg b.i.d. treatment, resulting effectively in a 2:1:1:1:2 randomization ratio (300 mg b.i.d.:150 mg b.i.d.: 75 mg b.i.d.: 25 mg b.i.d.: placebo) from the day of 450 mg b.i.d. discontinuation (20-Apr-2020) onward.

Randomization will be stratified by smoking status (current or ex-smoker) and severity of airflow limitation (FEV₁ \geq 30% to $<$ 50% and \geq 50% to $<$ 80%).

Figure 1-1 Study design

The primary endpoint will be assessed after 12 weeks of treatment.

Interim analyses (IA) on safety data are planned for an independent external safety data monitoring committee (DMC) to evaluate the results of pre-specified interim PK and safety data. Up to 5 DMC IAs are proposed to occur. Detailed information regarding DMC analysis will be provided in the DMC charter and a separate DMC SAP.

Up to 2 interim analyses (IAs) may be conducted on efficacy data. The purpose of the IA(s) is to have an early assessment of the efficacy data for planning future studies in the QBW251B program. The first IA will be triggered when approximately the first 645 to 680 randomized patients have either discontinued or completed 12 weeks of treatment. If the first IA does not lead to a clear decision for the planning of the QBW251B program, a second IA may be performed when all randomized patients have either discontinued or completed 12 weeks of treatment. The efficacy IA results will not trigger any design adaptations.

1.2 Study objectives and endpoints

Section 2 of the study protocol lists the following primary, key secondary, other secondary objectives.

Table 1-1 Objectives and related endpoints

Objective(s)	Endpoint(s)
Primary objective(s)	Endpoint(s) for primary objective(s)

 Characterize the dose-response relationship of QBW251 administered orally over 12 weeks on lung function, compared to placebo when added to inhaled triple combination therapy (long-acting β2-agonist/long-acting muscarinic receptor antagonist/inhaled corticosteroid; LABA/LAMA/ICS). 	
 Trough FEV₁ change from baseline after 12 weeks of treatment.
Secondary objective(s)	Endpoint(s) for secondary objective(s)

 Evaluate symptoms (overall COPD symptoms, cough and sputum) across various dose levels of QBW251 administered orally over 24 weeks, compared to placebo at Weeks 12 and 24. Evaluate health-related quality of life across various dose levels of QBW251 administered orally over 24 weeks, compared to placebo, at Weeks 12 and 24. Evaluate lung function across various dose levels of QBW251 administered orally over 24 weeks, compared to placebo, over 4, 8, 16, 20 and 24 weeks. Evaluate safety and tolerability across various dose levels of QBW251, administered orally over 24 weeks, compared to placebo. Assess the pharmacokinetics of QBW251 in COPD patients. Additionally this information may be used to understand the relation between drug exposure and efficacy and/or safety. 	
 Change from baseline in the Evaluating Respiratory Symptoms in COPD (E-RS) weekly mean scores (total and subscale scores). Change from baseline in Patient Global Impression of Severity (PGI-S) score. Change from baseline in the Cough and Sputum Assessment Questionnaire (CASA-Q) domain scores - cough symptoms, cough impact, sputum symptoms, and sputum impact. Change from baseline in St. George's Respiratory Questionnaire (SGRQ) total and domain scores at Weeks 12 and 24. Trough FEV₁ change from baseline after 4, 8, 16, 20 and 24 weeks of treatment, respectively. Assessment of ECGs, laboratory tests, vital signs, and adverse events per treatment group. Assessment of drug exposure (trough concentration; C_{min}) on all visits and around C_{max} on Days 1, 15 and 169. AUC and C_{max} on Days 1 and 15 in a sub-group of patients.

[REDACTED]	[REDACTED]
[REDACTED]	[REDACTED]
[REDACTED]	[REDACTED]
[REDACTED]	[REDACTED]
[REDACTED]	[REDACTED]

2 Statistical methods

2.1 Data analysis general information

All analyses will be performed by [REDACTED]. The most recent version of SAS available in the statistical programming environment of [REDACTED] will be used for the analysis.

Detailed information regarding DMC analysis will be provided in the DMC charter and a separate DMC SAP.

2.1.1 General definitions

The terms 'double-blind treatment' will be used in this document and refer to the double-blind QBW251 doses and Placebo.

2.1.1.1 Study day

Study day will be defined as the number of days since the date of first dose of double-blind treatment. The date of first dose of double-blind treatment will be defined as Day 1 and the day before the first dose of study drug will be defined as Day -1.

Therefore, for a particular date, study day will be calculated as follows:

for dates on or after the first date of double-blind treatment,

$$\text{Study day} = \text{Assessment date} - \text{Date of first dose of double-blind treatment} + 1;$$

for dates prior to the first date of double-blind treatment,

Study day = Assessment date – Date of first dose of double-blind treatment.

2.1.1.2 Baseline definition

In general, baseline is defined as the last measurement before the first dose of double-blind treatment. Details on calculation of baseline will be provided in the latter sections.

2.1.1.3 Post-baseline measurement

Post-baseline measurements are defined as those assessments after the first dose of double-blind treatment.

When change from baseline is of interest the following formula will be used for each scheduled visit and time-point where baseline and post-baseline values are both available:

Change from baseline = post-baseline value – baseline value.

If not stated otherwise for efficacy analyses on-treatment values are defined as values taken post-baseline but no later than 1 day after last dose of double-blind treatment. Off-treatment values are defined as post-baseline values taken more than 1 day after last dose of double-blind treatment.

For safety analyses other than adverse events (AEs), e.g. laboratory, ECG, vital signs, on-treatment values are defined as values taken post-baseline but no later than 30 days after last dose of double-blind treatment.

AEs will be considered as on-treatment if the event is starting on or after the time of first dose of double-blind treatment but not later than 30 days after last dose of double-blind treatment.

Details on calculation of post-baseline values are provided in the latter sections.

If not stated otherwise, visit-windows will be used for the data that is summarized by visit; they are based on the study evaluation schedule and comprise a set of days around the nominal visit day. For any assessment, there are the protocol defined scheduled visits around which visit windows were created to cover the complete range of days within the study. When visit windows are used, all visits will be re-aligned, i.e., they will be mapped into one of the visit windows. Details on calculation of visit windows will be provided in [Section 5](#).

2.1.1.4 Handling early termination of the 450mg b.i.d arm

If not stated otherwise, all efficacy inferential analyses will not include the 450 mg dose due to early termination of the 450 mg b.i.d arm, resulting in very few or no data in some of the strata (covariates/factors in the model) during the later visits. All descriptive summaries will include the 450 mg b.i.d. dose.

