The interim analyses are proposed to occur when 20%, 40%, 60%, 80%, and 100% of subjects have completed at least 4 weeks of treatment, which should be long enough to determine if the patient's exposure will exceed the threshold or not. The corresponding stopping boundaries in the p-value scale are 0.015, 0.016, 0.017, 0.018, and 0.019 for the interim analyses. For example, when the first interim analysis is performed after 20% patients have completed 4 weeks of treatment in the 450 mg b.i.d. arm, the observed (i.e. nominal) p-value has to be equal to or smaller than 0.015 in order to reject H_0 and terminate the treatment arm.

If the true proportion of patients in the 300 mg or 450 mg b.i.d. treatment arm exceeding the exposure threshold is < 5%, then the probability of rejecting H_0 would be very low (< 5%) with this group sequential test for the treatment arm. If the true proportion is 10% then the probability of rejecting H_0 and stopping the treatment arm early would be high ($\geq 77\%$). If the timing of the actual interim analyses deviate from the proposed schedule (20%, 40%, 60%, 80%, and 100% completed at least 4 weeks of treatment), stopping boundaries will need to be recalculated using the pre-specified α -spending function and based on the actual sample size at each interim analysis. The observed p-values at the interim analyses will then be compared against the recalculated stopping boundaries.

After reviewing the exposure data from the first interim analysis, the DMC informed the sponsor that the 450 mg b.i.d. arm had crossed the stopping boundary and recommended termination of the treatment arm. The DMC confirmed that the arm was well tolerated in this patient population and the stop was not based on adverse reactions to the 450 mg b.i.d. regimen.

The sponsor followed the DMC's advice and discontinued investigational treatment from all patients randomized to the 450 mg b.i.d. arm.

More detailed criteria will be outlined in the DMC charter.

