For each of the 11 candidate DR curves, a contrast test statistic will be derived that maximizes the power assuming the true mean response is the one assumed by the candidate DR curve. The detection of a significant DR signal is based on the maximum of the 11 contrast test statistics. The overall null hypothesis of no DR relationship is rejected if the multiplicity adjusted p-value for at least one contrast test is < 0.05 (one sided).

For each candidate DR curve, the test statistics and corresponding adjusted p-values will be presented.

Figure 2-1 Candidate Dose Response Curves

Due to termination of the 450 mg b.i.d. arm candidate curves Emax(ED50=300), SigEmax(ED50=300) and Exponential(delta=300) may no longer be appropriate for MCP-Mod analyses that do not include the 450 mg b.i.d. arm. These candidate curves will be removed and the Exponential(delta=75) will be added.

Step 2 (Estimation of the dose-response curve and target dose – Mod part):

Once the DR signal is declared, the DR curve and the target dose(s) of interest will be estimated by model averaging. A large number of bootstrap samples from the multivariate normal distribution will be drawn with adjusted means from the MMRM and corresponding covariance matrix. For each sample:

- DR models from the candidate families (Emax, Sigmoid Emax, Exponential, Linear) will be fitted to the data and the best model according to the generalized Akaike information criterion (AIC) will be chosen.
- The predictions for dose-response will be obtained from the best model for each sample.

The final DR curve estimate is the median of these predictions while confidence intervals will be calculated from the quantiles. The final DR curve estimate with the model-based two-sided 90% confidence interval will be presented graphically. In addition, the plot will include the mean responses from the MMRM and the associated 90% confidence intervals for each of the studied dose groups.

The target dose(s) that corresponds to a clinically relevant effect over placebo can be estimated using inverse regression techniques ([Bretz et al 2005](#)). The target dose will be estimated for a delta of 50ml and presented graphically within the estimated DR curve.

All data related to safety, efficacy and other assessments including PK exposure will be taken into consideration to propose a dose for Phase 3.

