2.8.1 Adverse events (AEs)

The on-treatment period for adverse events lasts from the date of first administration of double-blind study treatment to 30 days after the date of the last actual administration of double-blind

study treatment. Adverse events will be summarized by treatment group. Summary tables for AEs will summarize only on-treatment events (also known as treatment-emergent AEs).

The number (and percentage) of subjects with treatment-emergent adverse events will be summarized in the following ways:

- by treatment and preferred term (PT).
- by treatment, primary system organ class (SOC) and PT.
- by treatment, SOC, PT and maximum severity.

Separate summaries by SOC and PT will be provided for:

- AEs suspected to be study medication related
- fatal AEs
- leading to treatment discontinuation
- leading to dose interruptions and/or adjustments
- serious adverse events (SAEs)

Further SAEs will be summarized by PT.

In addition, treatment emergent AEs and SAEs will be presented by treatment, system organ class and preferred term, showing exposure adjusted event rates (i.e., the number of events expressed in rates per 100 patient years).

Unless otherwise specified, SOCs will be sorted alphabetically and, within each SOC, the PTs will be sorted in descending order of frequency in the highest QBW251 dose. A subject with multiple adverse events within a SOC or PT is only counted once towards the total of the SOC or PT.

Listings will be provided for all AEs, SAEs and fatal AEs.

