2.8.3 Laboratory data

Summaries of laboratory data will include on-treatment measurements, which are defined as measurements taken post-baseline but no later than 30 days after last dose of double-blind treatment.

Absolute values and change from baseline will be summarized for continuous laboratory parameters by visit, including the worst on-treatment value. The direction of interest for worst on-treatment value for selected hematology and biochemistry parameters is shown in [Section 5.4](#).

For selected laboratory tests, the number and percentage of patients with newly occurring or worsening laboratory abnormalities meeting the clinically notable criteria at any time on-treatment, considering all on-treatment data from scheduled, unscheduled and premature discontinuation visits, will be summarized by laboratory parameter. Notable criteria are defined in [Section 5.4](#).

Furthermore, the number and percentage of patients with newly occurring or worsening abnormalities in liver function tests (LFT) will be summarized by treatment and at any time on-treatment considering all on-treatment data from scheduled, unscheduled and premature discontinuation visit. LFT criteria are defined in [Section 5.4](#).

The baseline value is the last value prior to first dose of double-blind treatment.

For selected laboratory parameter boxplots of laboratory values relative to the normal ranges will be provided.

Laboratory data of patients with notable values will be listed. Urinalysis will be listed for patients with abnormal urine dipstick.

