2.8.4 Other safety data

2.8.4.1 ECG and cardiac imaging data

Summaries of ECG data will include on-treatment measurements, which are defined as measurements taken post-baseline but no later than 30 days after last dose of double-blind treatment. Triplicate ECGs (3 ECGs are collected within about a five-minute window) will be performed. For the analysis of continuous ECG parameter the mean value of the 3 ECG measurements will be used, for ECG interpretation, all findings of the 3 ECGs will be considered.

Absolute values and change from baseline will be summarized for ECG parameters by visit and time point. The maximum on-treatment QTc value will be included in the summary.

The number and percentage of patients with newly occurring or worsening notable Fridericia's QTc values will be summarized at any time on-treatment, considering all on-treatment data from scheduled, unscheduled and premature discontinuation visits. For derivation of notable values, the mean of the triplicate ECGs will be used. Notable criteria are defined in [Section 5.5](#).

The number and percentage of patients with ECG abnormalities will be summarized by evaluation type, abnormality finding, visit and time point.

The baseline value is the last value prior to first dose of double-blind treatment.

ECG data of patients with notable Fridericia's QTc values will be listed.

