2.8.4.2 Vital signs

Summaries of vital signs data will include on-treatment measurements, which are defined as measurements taken post-baseline but no later than 30 days after last dose of double-blind treatment.

Absolute values and change from baseline will be summarized for vital sign parameters by visit including the minimum and maximum on-treatment value.

The number and percentage of patients with newly occurring or worsening notable vital sign values will be summarized at any time on-treatment, considering all on-treatment data from scheduled, unscheduled and premature discontinuation visits. Notable criteria are defined in [Section 5.5](#).

The baseline value is the last value prior to first dose of double-blind treatment.

Vital sign data of patients with notable values will be listed.

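### Worst-value, any-time and crude AE tables compare the early-stopped 450 mg arm with 24-week arms without a common time window, so they tend to show fewer findings at 450 mg

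*SAP*

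**What the plan says.** The first DMC interim analysis found that the 450 mg arm had crossed its exposure-based boundary. Protocol 12.7.1 records the consequence: "The sponsor followed the DMC's advice and discontinued investigational treatment from all patients randomized to the 450 mg b.i.d. arm". Protocol 3 and SAP 1.1 date the arm's discontinuation to 20-Apr-2020. About 102 patients had been randomised to it.

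SAP 2.1.1.4 removes 450 mg from efficacy inference because of the early stop, "resulting in very few or no data in some of the strata (covariates/factors in the model) during the later visits". It then adds: "All descriptive summaries will include the 450 mg b.i.d. dose".

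The safety summaries affected are:

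- **Laboratory (SAP 2.8.3):** "continuous laboratory parameters by visit, including the worst on-treatment value", plus counts of notable laboratory and liver findings at any time on treatment.
- **ECG (SAP 2.8.4.1):** "The maximum on-treatment QTc value will be included in the summary", plus notable QTcF values at any time on treatment.
- **Vital signs (SAP 2.8.4.2):** "by visit including the minimum and maximum on-treatment value", plus notable values at any time on treatment.
- **AEs (SAP 2.8.1):** "The number (and percentage) of subjects with treatment-emergent adverse events will be summarized in the following ways", with further crude tables by severity, relatedness, fatal outcome and discontinuation.

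SAP 2.1.1.3 counts safety data as on-treatment up to 30 days after the last dose. Exposure-adjusted event rates are planned for AEs and SAEs (SAP 2.8.1) and for AEs of special interest (SAP 2.8.1.2). Duration of exposure is summarised by arm (SAP 2.4.1).

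**The concern.** Observation ended early in one arm only. A maximum, a minimum, an any-time count or a crude percentage increases with the time and number of readings available. An arm cut short therefore tends to look better on these statistics even when its underlying rates equal those of the other arms.

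The SAP handles the same imbalance on the efficacy side: the supportive dose-response analysis that brings 450 mg back in uses data only to Week 12 (SAP 2.5.4). The safety sections contain no equivalent restriction. The truncated arm also sets the order of the AE tables, because preferred terms are sorted by their frequency in the highest dose.

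These tables matter for dose selection. SAP 2.5.2 says: "All data related to safety, efficacy and other assessments including PK exposure will be taken into consideration to propose a dose for Phase 3". Protocol 4.5 notes that a formal thorough QT assessment has not been completed. A rising trend in QTcF, liver tests or AEs across the dose range could be flattened at the top dose by short follow-up alone.

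**Working it through.** The documents give no figure for this bias and no exposure times for the 450 mg arm. The size is therefore shown under stated assumptions.

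**Inputs from the documents.** Treatment lasts 24 weeks = 168 days. The on-treatment window adds 30 days, so full follow-up is 198 days. About 102 patients were on 450 mg. Allocation before the stop was 2:2:1:1:1:2.

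**Assumptions.** 450 mg patients were accrued uniformly over A weeks before the stop, with A from 16 to 48. The hazard is constant and equal in all arms. All arms have the 30-day window and there is no other dropout.

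**1. Time on drug.** T = min(time since randomisation, 24 weeks). For A = 16, mean T = 16/2 = 8 weeks. For A = 48, half the patients average 12 weeks and half complete 24, so mean T = 18 weeks.

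**2. Crude AE percentage.** Take 60% at full follow-up: h = -ln(0.4)/198 = 0.004628 per day. The 450 mg percentage is 1 - exp(-30h) × E[exp(-hT)], with exp(-30h) = 0.870.

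- A = 16 weeks (112 days): E[exp(-hT)] = (1 - exp(-112h))/(112h) = 0.780. Result: 1 - 0.870 × 0.780 = 32%.
- A = 48 weeks: E[exp(-hT)] = 0.5 × 0.695 + 0.5 × 0.460 = 0.577. Result: 1 - 0.870 × 0.577 = 50%.

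Accrual over 24 and 36 weeks gives 40% and 46%.

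**3. Fixed time on drug.** With w weeks on drug and an event seen in a proportion p at full follow-up, the 450 mg figure is 1 - (1 - p)^((7w + 30)/198). The masked hazard ratio, 198/(7w + 30), is the true excess at 450 mg that would look no worse than the other arms.

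| Weeks on drug | 10% event shows as | 30% event shows as | Masked hazard ratio |
|---|---|---|---|
| 4 | 3.0% | 9.9% | 3.4 |
| 8 | 4.5% | 14.4% | 2.3 |
| 12 | 5.9% | 18.6% | 1.7 |
| 16 | 7.3% | 22.6% | 1.4 |

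**4. Maximum QTc and any-time notable QTcF.** A completer has 11 post-baseline ECG sets: Day 1 post-dose, Week 2 pre- and post-dose, Weeks 4, 8, 12, 16 and 20, Week 24 pre- and post-dose, and Follow-Up (Day 197, 28 days after Day 169). I give each stopped patient the sets reached before the stop plus one discontinuation set. With independent readings from the same distribution, the expected maximum is lower at 450 mg by 0.44 within-patient SD (A = 16) to 0.17 SD (A = 48). With one further set inside the 30 days, the gap is 0.32 to 0.12 SD. A finding with an assumed 1% chance per reading appears in 1 - 0.99^11 = 10.5% of completers. With one discontinuation set, it appears in 5.1% to 8.3% of 450 mg patients.

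**5. Exposure-adjusted rates.** The SAP does not say whether person-time includes the 30 days in which events are counted. If the denominator is drug days only, equal hazards give 450 mg a rate of [(7w + 30)/(7w)]/(198/168) relative to a 24-week arm: 1.76 at 4 weeks, 1.30 at 8 and 1.15 at 12. That error runs in the opposite direction from the crude tables.

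**6. Concurrent comparators.** 102/2 × (2 + 1 + 1 + 1 + 2) = 357 patients outside 450 mg, by planned ratio.

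**The case against.** The plan already contains partial remedies. AEs, SAEs and AEs of special interest get exposure-adjusted rates, and exposure and discontinuation reasons are tabulated by arm. Laboratory, ECG and vital-sign data are summarised by visit. In particular, the Day 1 and Day 15 post-dose ECGs give a time-matched comparison that includes 450 mg. All of this stands and limits the harm. It does not reach the any-time and worst-value laboratory, liver, QTcF and vital-sign tables, which have no exposure-adjusted or time-limited counterpart.

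Four stronger readings are tempting, and the documents do not support them:

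- **The top dose looks safer by construction.** This is a tendency that depends on event rates being similar over time. Early clustering of events weakens it, and the exposure-adjusted rates can err upwards.
- **450 mg data end on the day drug stopped.** On-treatment data run 30 days further and include premature discontinuation visits. The calculations above allow for this.
- **450 mg here is the only direct safety evidence above 300 mg.** Protocol 4.2 cites an earlier cystic fibrosis study at 450 mg b.i.d., and SAP 5.6.10 lists 8 + 23 + 39 = 70 subjects given 450 or 750 mg twice daily. The statement holds only within this trial.
- **450 mg should leave the main tables.** They are defined on the Safety Set, to which these treated patients belong, and removing the arm would also lose its 30-day post-dose data. Neither is necessary.

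The comparator arms will also have dropout; the sample-size section assumes 20%. If those patients left uniformly over 24 weeks, the comparator figure of 60% would fall to 0.8 × 60% + 0.2 × 39.5% = 55.9%. The gap narrows but remains.

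**Conclusion.** The point holds as an imbalance of follow-up in specific descriptive tables. As written, the plan compares 450 mg with longer-observed arms on statistics that increase with observation time, and it sets no common window. Under a constant, equal hazard and accrual over 16 to 48 weeks, a 60% AE incidence would read about 32% to 50% at 450 mg. Any-time and worst-value findings shift in the same direction. The size is illustrative, because actual exposure times, event rates and reading variability are not in the documents. The direction is a tendency, not a certainty. The primary efficacy analysis is unaffected. The change is worth making because these tables contribute to the Phase 3 dose proposal and the correction needs no new data.

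**What to change.** In SAP 2.1.1.4 and 2.8:

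1. Keep 450 mg in the main Safety Set tables, with a footnote giving its duration of exposure.
2. Add a companion version of the worst-value, minimum/maximum, any-time-notable and crude AE and SAE tables. Restrict it to patients randomised before 20-Apr-2020 and apply the same calendar cut, at the 450 mg stop, to every arm. Randomisation then gives all arms comparable follow-up. State the cut date explicitly, because individual last-dose dates are not in the documents.
3. State that between-dose comparisons involving 450 mg rest on the companion tables.
4. Define the person-time in the exposure-adjusted rates so that it covers the same 30-day window as the events counted.

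By-visit summaries can stay as they are. The cost is SAP wording and one rerun of existing tables. The downside is that the companion tables use only concurrently randomised patients, about 357 outside 450 mg by planned ratio, with shorter follow-up. The cut also leaves out data after the stop, which the main tables retain.
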